8. STATISTICAL METHODOLOGY

8.1. Study Subjects

8.1.1. Subject Disposition

Subject disposition will be summarized on the SAF and listed on the enrolled subjects.

8.1.2. Analysis Populations

Analysis populations will be summarized and listed on the enrolled subjects. The listing will include the inclusion and exclusion criteria deviation at screening.

8.1.3. Exposure

Exposure data will be listed on the SAF.

8.1.4. Demographic and Other Baseline Characteristics

The following demographic and other baseline characteristics will be used.

	Category	descriptive
Sex	Male, Female	
Age at informed consent(years)		Yes
Height(cm)		Yes
Weight(kg)		Yes
BMI(kg/m ²)		Yes
Race	Japanese	
ALS type	Limb type, Bulbar type	
Day of onset(years)		Yes
EI Escorial Revised Airlie House criteria	Clinically definite ALS, Clinically probable ALS, Clinically probable-laboratory-supported ALS	
Total ALSFRS-R score		Yes
Medical history	No, Yes	
Complication including constipation	No, Yes	
Constipation	No, Yes	
Concomitant medication	No, Yes	
Concomitant therapies	No, Yes	
Allergic history (including drug allergies)	No, Yes	
Drinking status	No (if 'Never'), Yes (if otherwise)	
Smoking status	No (if 'Never'), Yes (if otherwise)	
Edaravone history	No, Yes (if any record at "Edaravone Intravenous History")	

Demographic and other baseline characteristics will be summarized and listed on the SAF.

ALSFRS-R score of each item will be listed on the SAF.

8.1.5. Meal Condition

Meal condition will be listed on the SAF.

8.1.6. Medical History and Allergic History

Medical history and allergic history will be listed on the SAF.

8.1.7. Prior or Concomitant Medications/ Therapies

Prior medication and concomitant medication/ therapies will be listed on the SAF.

8.2. Efficacy Assessments

N/A

8.3. Safety Assessments

Safety assessments will be made on the SAF.

8.3.1. Adverse Events

Overall summary for the following will be conducted.

- Subjects with at least one TEAE
- Subjects with at least one adverse drug reaction
- Subjects with at least one TESAE
- Subjects with at least one serious adverse drug reaction
- Subjects with discontinuation due to TEAE
- Subjects with TEAE leading to death

The following summaries also will be conducted. These table will be ordered by International Agreed Order for SOC and then by alphabet order for PT.

- TEAEs by SOC and PT
- Adverse drug reactions by SOC and PT
- TEAEs by SOC, PT and severity
- TEAEs by SOC, PT and Causal Relationship to the Investigational Product

Each of the summaries will be done at the subject level - multiple occurrences of the same event within a subject will be counted once in the summaries by SOC and PT; multiple occurrences of the same event within a subject will be counted once in the maximum severity category (severe > moderate > mild) and/or maximum drug relationship category (reasonable possibility/no reasonable possibility).

All AEs, TEAEs, ADR, SAEs and TESAEs will be listed.

8.3.2. Laboratory Tests

Absolute values and changes from baseline, except for qualitative urinalysis will be

summarized by scheduled visit.

For urinalysis except for specific gravity, number and percentage will be presented. Shift tables will present the changes in clinically relevant categories from baseline to each scheduled post-baseline visit.

Below is a list of the laboratory test.

Laboratory Test	Parameters
Hematology	Hemoglobin, hematocrit, red blood cell count, white blood cell count, platelet count, MCH, MCHC, MCV, differential white blood count
Biochemistry	Na, K, Cl, Ca, inorganic phosphorus, urea nitrogen, creatinine, uric acid, total bilirubin, direct bilirubin, ALT, AST, γ -GTP, ALP, LDH, CK, amylase, total cholesterol, triglycerides, LDL-C, HDL-C, total protein, albumin, glucose, FSH (listing only)
Urinalysis	Quantitative (specific gravity), qualitative (pH, protein, glucose, occult blood, urobilinogen, bilirubin, ketones), sediment (listing only), hCG (listing only)

All data including clinically relevant flagged will be listed.

8.3.3. Vital Signs

Absolute values and changes from baseline will be summarized for the following parameters by scheduled visit.

- Systolic Blood Pressure (mmHg)
- Diastolic Blood Pressure (mmHg)
- Pulse Rate (beats/min)
- Body Temperature($^{\circ}$ C)

Vital signs data will be listed.

8.3.4. 12-Lead ECGs

Absolute values and changes from baseline will be summarized for the following parameters by scheduled visit.

- Heart Rate (beats/min)
- QTcF (msec)
- PR (msec)
- QT (msec)
- RR (msec)
- QRS (msec)

The percentage of subjects with 12-lead ECG values outside pre-defined limit will be summarized by scheduled visit. The ECGs will be assessed by the investigator and deemed

“Normal”, “Abnormal, not clinically significant” (Abnormal, NCS) and “Abnormal, clinically significant” (Abnormal, CS) and tabulated by scheduled visit using frequency counts and percentages.

12-Lead ECG data (including overall evaluation) will be listed.

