**(2) Objective findings**

The investigator (or subinvestigator) will identify any clinically significant abnormal finding\* and handle it as an AE.

\* “Clinically significant abnormal findings” will be identified according to the following criteria.

- Relationship to clinical signs or symptoms

If these symptoms or signs are reported as AEs, the related abnormal laboratory findings and other test results will not be reported as separate AEs.

- Medical or surgical treatment of the abnormal laboratory test findings and other test results
- If the investigator (or subinvestigator) judges the abnormality as clinically significant for other reason(s).

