### 13.4.3 Safety

(1) Adverse events and adverse drug reactions

Adverse events will be coded according to the Medical Dictionary for Regulatory Activities (MedDRA) (version 22.0 or later). The number and proportion of subjects with treatment-emergent adverse events (TEAEs) which emerge newly after having treatment or worsen relative to the pre-treatment, and adverse reactions of TEAEs will be calculated. Adverse events that occurred will be listed regardless of whether the investigational product was administered.

(2) Vital signs and laboratory tests

For vital signs (systolic and diastolic blood pressure, pulse rate, and body temperature) and

Confidential

laboratory data (hematology, biochemistry, and urinalysis), descriptive statistics will be calculated for the values at each time point and the changes from baseline. The values of urinalysis will be presented in a shift table.

(3) 12-lead ECG

Descriptive statistics of the values at each time point and the changes from baseline will be calculated for 12-lead ECG.

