6. STATISTICAL CONSIDERATIONS

6.1. Descriptive Statistics

(1) Non-PK related

Continuous data will be summarized descriptively using the number in the analysis set (N), the number of observations (n), mean, standard deviation (SD), median, minimum and maximum. Categorical data will be summarized using frequency counts and percentages. The denominator for the percentages will be the total number of subjects and analysis population being presented, unless otherwise specified.

(2) PK related

(a) Plasma concentrations

Plasma concentrations will be summarized descriptively using N, n, mean, SD, CV%, median, minimum and maximum.

(b) Pharmacokinetic parameters

The plasma and urine PK parameters will be summarized descriptively using N, n, arithmetic mean, SD, median, CV%, range (minimum, maximum), geometric mean and geometric CV%. For Ae, Ae% and CLr, geometric mean and geometric CV% will be calculated only when all the individual Ae, Ae% and CLr is greater than 0 in each sampling time point.

CV% and Geometric CV% will be calculated as follows:

$$CV\% = \frac{\text{standard deviation}}{\text{arithmetic mean}} \times 100$$

$$\text{Geometric CV\%} = \sqrt{[\exp(\sigma^2) - 1]} \times 100$$

where σ represents the standard deviation computed on the natural logarithmic transformed concentrations.

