7.2. Analysis Visit Definitions

(1) Non-PK related

The date of the first dose of investigational product is defined as Day 1.

Unless otherwise specified, baseline will be the last observed value of the parameter of interest prior to the first intake of investigational product (this includes unscheduled visits).

Tests	Analysis visit	Nominal day/Time point	Window
Vital signs 12-lead ECG	Screening	Day -30 to Day -2	-
	Day -1	Day -1	-
	Day 1	Before initiation of study treatment on Day 1	-
	Day 2	24 hours after initiation of study treatment	Nominal time point \pm 3 hours
Laboratory tests	Screening	Day -30 to Day -2	-
	Day -1	Day -1	Day -2 to Day -3 when subjects who are hospitalized throughout the study undergo a preliminary test between Day -2 and Day

Tests	Analysis visit	Nominal day/Time point	Window
			-3. Day -1 if otherwise.
	Day 2	Day2	-

(2) PK related

The allowable time window will be the following.

Plasma PK sampling

Nominal Time Point	Window
Predose	Within 60 min before dosing
0.25, 0.5, 1, 2, 4, 8 h after dosing	Nominal time point \pm 5 min
24 h after dosing	Nominal time point \pm 15 min

Urine PK sampling

Nominal Time Point	Window
Predose	Within 60 min before dosing
Voluntary Urine	—
Forced micturition at 8 h after dosing	Nominal time point \pm 30 min

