9.3. Analysis Visits to Report

(1) Non-PK related

Safety:

	Apply to		
Analysis Visit	Laboratory Tests	Vital Signs	12-Lead ECGs
Screening	X	X	X
Day -1	X	X	X
Day 1		X	X
Day 2	X	X	X
Follow up	X	X	X

Pre-baseline, unscheduled visits and retests (same visit number assigned) will not be displayed in by-visit summary tables, but will be included in the data listings.

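### The QTcF-limit, ECG-category and shift tables count scheduled visits only, so an out-of-limit post-dose value found only at an unscheduled test enters no ECG or laboratory summary table

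*SAP*

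**What the plan says.** SAP 7.1.2.3 sets numeric QTcF bands (above 450, 480 and 500 msec, and 450 or below) and two change limits (more than 30 and more than 60 msec). SAP 8.3.4 tabulates them per visit: "The percentage of subjects with 12-lead ECG values outside pre-defined limit will be summarized by scheduled visit". The investigator's normal/abnormal ECG rating is tabulated in the same way.

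For laboratory tests, SAP 8.3.2 says: "Shift tables will present the changes in clinically relevant categories from baseline to each scheduled post-baseline visit". The scope of that sentence is not certain. It directly follows one on urinalysis, and Protocol 13.4.3 plans such a table for urinalysis alone: "The values of urinalysis will be presented in a shift table".

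SAP 9.3 then limits what a per-visit table may contain: "Pre-baseline, unscheduled visits and retests (same visit number assigned) will not be displayed in by-visit summary tables". These values stay in the listings. No any-post-dose or worst-value summary is planned.

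Two neighbouring rules matter. SAP 7.2 lets an unscheduled value before dosing serve as baseline. Protocol 13.3(2) takes the later of several values that fall in one time window.

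For percentages outside the PK analyses, SAP 6.1 sets a default: "The denominator for the percentages will be the total number of subjects and analysis population being presented, unless otherwise specified". SAP 8.3.2 and 8.3.4 name no other denominator, while SAP 7.3 bases safety summaries on observed data without imputation.

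**The concern.** ECG and laboratory tests are two of the four safety endpoints. A table of QTcF limits is there to show how many subjects crossed a numeric threshold after dosing. Under these rules it shows only how many crossed it at one of two planned visits. An extra ECG taken because something seems wrong is the one most likely to find a crossing, and it is the one left out.

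The treatment is also uneven: an unscheduled value can set a subject's baseline, but an unscheduled value after dosing cannot count against a limit. A reader of the summary tables alone could see 0% above a limit while a listing holds a post-dose value above it.

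**Working it through.** The plan gives no figure to reproduce. N = 9 is stated not to rest on a statistical calculation, and the safety analyses are descriptive. The check is of which values can reach which table, and then of size.

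**Step 1: which post-dose ECGs are scheduled.** Protocol 9.2.5.1(3) places them at 24 h and at the end-of-study or withdrawal assessment. SAP 7.2 gives the 24 h point a window of ±3 h, so it runs from 24 − 3 = 21 h to 24 + 3 = 27 h. Apart from a withdrawal assessment, any ECG before 21 h, or between 27 h and the end-of-study visit, is unscheduled. Protocol section 1(3) reports peak plasma concentration at 0.4 to 0.8 h for the fasted suspension in Study MT-1186-J01, so an ECG near peak exposure is always unscheduled. Post-dose laboratory tests are scheduled on Day 2 and at end of study, so a test between those visits is unscheduled too.

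**Step 2: where an out-of-limit post-dose value appears.** This combines SAP 8.3.1, 8.3.2, 8.3.4 and 9.3 with Protocol 9.2.5.2.

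| Value found at | ECG or laboratory summary table | TEAE tables | Listings |
|---|---|---|---|
| Scheduled visit | Yes | If judged clinically significant, or through a related symptom | Yes |
| Unscheduled test, judged clinically significant | No | Yes | Yes |
| Unscheduled test, related symptom reported as AE | No | Symptom only | Yes |
| Unscheduled test, neither of these | No | No | Yes |

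The third row follows from Protocol 9.2.5.2(2): when the symptom is reported, "the related abnormal laboratory findings and other test results will not be reported as separate AEs". The subject is counted, but the table shows the symptom and not the QTcF or laboratory value.

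**Step 3: size of the omission.** Assume one subject whose only out-of-limit value is at an unscheduled test. The per-visit table shows 0/N; an any-post-dose row shows 1/N.

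- N = 9: 0/9 = 0% against 1/9 = 11.1%.
- N = 6 (the minimum that SAP section 1 treats as evaluable): 0/6 = 0% against 1/6 = 16.7%.

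**Step 4: denominator.** With k subjects out of limit and m not measured at the visit, the SAP 6.1 default gives k/N, and subjects measured gives k/(N − m). For k = 1, both k and m being assumptions:

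| N | m | k/N | k/(N − m) | Difference (points) |
|---|---|---|---|---|
| 9 | 0 | 11.1% | 11.1% | 0 |
| 9 | 1 | 11.1% | 12.5% | 1.4 |
| 9 | 3 | 11.1% | 16.7% | 5.6 |
| 6 | 1 | 16.7% | 20.0% | 3.3 |
| 6 | 3 | 16.7% | 33.3% | 16.7 |

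**Step 5: retests.** For two ECGs inside the 21 to 27 h window, Protocol 13.3(2) uses the second, whereas SAP 9.3 keeps a retest out of the table. SAP section 1 gives the SAP precedence on analysis details. Protocol 13.5, however, requires changes to its analysis section to be recorded with reasons, and SAP section 10 records only the one on specific gravity.

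**The case against.** The strongest reply is that the AE tables and the listings already cover this. A clinically significant abnormal finding must be handled as an AE, and TEAE tables are not tied to scheduled visits. A symptom that prompts an ECG normally puts the subject in those tables. The ALT and AST increases in Study MT-1186-J02 and the occult blood finding in MT-1186-J04 were reported as adverse events. With 6 to 9 subjects, every listed value can be read. Subjects are in hospital from Day -1 to Day 2, so a missed 24 h assessment is unlikely. The study has a PK objective and no safety decision rule.

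Most of this stands, and it rules out four stronger readings:

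- **That such a value enters no safety summary at all.** It can reach the TEAE tables by the routes in Step 2.
- **That the error always makes the drug look safer.** If a high scheduled value is normal on retest, leaving out the retest keeps the high value in the table.
- **That a laboratory shift such as ALT would be hidden in the shift table.** That table may be for urinalysis only. The low/high/abnormal flags in SAP 7.1.2.2 leave a wider scope possible but do not establish it.
- **That an unmeasured subject is counted as normal.** The band at or below 450 msec and the normal rating are categories of their own. An unmeasured subject falls in neither, so the counts visibly fall short of N. QTcF is also summarised with both N and n. Only the rows for change above 30 and 60 msec have no complementary category.

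The objection leaves one gap. The QTcF limits are numeric and do not depend on judgement, so a table built on the investigator's judgement cannot replace them. A value judged not significant, with no related symptom reported, is found in listings only.

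**Conclusion.** The concern holds in a limited form. An out-of-limit post-dose value found only at an unscheduled test enters no ECG or laboratory summary table, and it reaches the TEAE tables only through clinical significance or a reported symptom. One such subject moves the reported percentage by 11.1 points at n = 9 or 16.7 at n = 6. This assumes that at least one such test occurs. The documents give no count of unscheduled tests, and with none there is no effect.

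The denominator is a minor addition. It matters only if a visit is missed, and mainly for the two change rows. For one unmeasured subject and one event the difference is 1.4 points (n = 9) or 3.3 points (n = 6).

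This is an inexpensive improvement of modest weight, and it does not affect the PK objective.

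**What to change.** 1. In SAP 8.3.2 and 8.3.4, add to the shift tables and the QTcF-limit table one row labelled as any post-dose, including unscheduled and repeat tests. Define it per subject as the worst value over all post-dose tests. In SAP 9.3, exempt this row from the exclusion.
2. State whether the shift tables cover urinalysis only or all flagged laboratory tests.
3. Reconcile the retest rule in SAP 9.3 with the later-value rule in Protocol 13.3(2). If they are meant to differ, record that and the reason in SAP section 10.
4. In SAP 6.1, state that by-visit ECG and laboratory percentages use subjects with a value at that visit, and also a baseline value for change and shift.

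The cost is SAP wording and one extra row per table, with no new data. The downside is that the added row includes symptom-triggered tests and may look slightly less favourable, which is why it needs the label.

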8.3.5. Physical Examinations

Physical examination will be listed.

8.4. Pharmacokinetics Evaluation

8.4.1. Concentrations for unchanged edaravone, sulfate conjugate, and glucuronide conjugate

(1) Summary tables and listings

Plasma and urine unchanged edaravone, sulfate conjugate, and glucuronide conjugate concentrations will be summarized at each nominal sampling point. All plasma concentrations will also be listed.

(2) Individual plasma concentration plots

Individual plasma concentrations vs. actual time for unchanged edaravone, sulfate conjugate, and glucuronide conjugate will be plotted on both linear/linear and log/linear scales.

(3) Mean plasma concentration plots

Mean plasma concentrations vs. nominal time curves will be plotted on both linear/linear (+SD) and log/linear scales.

8.4.2. Pharmacokinetic Parameters for unchanged edaravone, sulfate conjugate, and glucuronide conjugate

The PK parameters listed in Section 2.3 will be calculated for each subject using non-compartmental model. The PK parameters will be listed and summarized. The PK parameters listed as other PK parameters will not be summarized.

The urinary pharmacokinetic parameters will be listed and summarized. The urinary pharmacokinetic parameters at pre-dose will not be summarized.

9. DATA PRESENTATION CONVENTIONS

9.1. Number of Digits to Report

(1) Non-PK related

Statistic	Specification	Apply to
Minimum, Maximum	Same number of DPs as the data provided in the datasets	All original (i.e. non-derived)
	see section 7.1	All derived data
Mean, Median, SD, SE, Confidence intervals	One more DP than above	All
Percentages ^{*1}	1 DP	All
Ratios	3 DPs	All

*1 Percentages: use 1 place beyond the DP, except for the following cases:

If the percentage is equal to 0, then leave blank, do not use (0)

If the percentage is equal to 100, then use "(100)" without a decimal

(2) PK Plasma Concentration

Statistic	Specification
Individual value	The same significant digits as they are reported
Mean, SD, Minimum, Median, Maximum	The same significant digits as they are reported
CV%	1 DP

(3) PK Parameters

Statistic	Specification
Individual value Mean, SD, Minimum, Maximum, Median, Geometric mean	C_{\max} : same significant digits as they are reported t_{\max} : 2 DPs $t_{1/2}$: 2 DPs k_{el} : 4 DPs Other parameters to be summarized: 3 significant digits Summary statistics will be calculated with the individual values before being rounded off, and then be rounded off to the designated digits. $AUC\%_{ex}$: 3 DPs Adjusted R^2 : 3 DPs Number of k_{el} points: 0 DP Lower and Upper limited of k_{el} : 2 DPs
CV%, Geometric CV%	1 DP

9.2. Treatments to Report

Treatment	For TFLs
MT-1186	Edaravone

9.3. Analysis Visits to Report

(1) Non-PK related

Safety:

	Apply to		
Analysis Visit	Laboratory Tests	Vital Signs	12-Lead ECGs
Screening	X	X	X
Day -1	X	X	X
Day 1		X	X
Day 2	X	X	X
Follow up	X	X	X

Pre-baseline, unscheduled visits and retests (same visit number assigned) will not be displayed in by-visit summary tables, but will be included in the data listings.

10. CHANGE FROM THE PROTOCOL

Specific gravity will be summarized for absolute value and change from baseline as quantitative value. This is because it was planned as qualitative test in the protocol, but it was as quantitative test actually.

11. SOFTWARE

All statistical analyses will be performed using SAS version 9.4 or higher.

The PK parameters will be calculated using WinNonlin® software (version 6.3 or later).

[figure not shown]

Appendix 1 Pharmacokinetic Parameter Calculations

PK Parameter Calculations		
Parameters	Unit	Calculation
AUC _{0-x} AUC _{0-t}	ng·h/mL	
AUC will be calculated using the linear trapezoidal method and actual times
 $AUC_{t_0-t_n} = \sum_{i=1}^{t_n} \frac{t_i - t_{i-1}}{2} (C_{i-1} + C_i)$ 
AUC_{0-t} will be calculated as AUC when t_0 is set to time zero and t_n is set to t (the last quantifiable concentration time point).
 
AUC_{0-x} will be calculated as AUC when t_0 is set to time zero and t_n is set to X.

AUC _{0-∞}	ng·h/mL	$AUC_{0-\infty} = AUC_{0-t} + C_{last} / k_{el}$ 
C_{last}: last measurable concentration

AUC% _{ex}	%	$AUC\%_{ex} = (AUC_{0-\infty} - AUC_{0-t}) / AUC_{0-\infty} \times 100$
C ₀	ng/mL	will be estimated using a log-linear regression of first two data points to back-extrapolate C ₀
C _{ave}	ng/mL	$C_{ave} = AUC_{0-t} / \tau$ 
τ: dosing interval

C _{max}	ng/mL	will be determined by visual inspection
CL/F	L/h	
(single dose)
 $CL/F = \text{Dose} / AUC_{0-\infty}$ 
(steady state)
 $CL_{ss}/F = \text{Dose} / AUC_{0-t}$
t _{max}	h	Measured time of C _{max}
t _{1/2}	h	t _{1/2} will be determined as: $t_{1/2} = \log_e(2) / k_{el}$
k _{el}	/h	
The exponential rate constant of the terminal phase, k_{el}, will be estimated by log-linear regression, if determinable. The number of data points included in the regression will be determined by visual inspection. Wherever possible, a minimum of 3 data points will be used in the estimation of k_{el}.
 
During the analysis, this calculation method repeats regressions using the last three points with non-zero concentrations, then the last four points, last five, etc. The time of maximum concentration (t_{max}) will be excluded from the estimation of k_{el}.

		
Points with a value of zero for the dependent variable are excluded. For each regression, an adjusted R^2 is computed
 $\text{Adjusted } R^2 = 1 - \frac{(1-R^2) \times (n-1)}{(n-2)}$ 
where n is the number of data points in the regression and R^2 is the square of the correlation coefficient.
 
The regression with the largest adjusted R^2 is selected to estimate k_{el}, with these caveats:
 
 - If the adjusted R^2 does not improve, but is within 0.0001 of the largest adjusted R^2 value, the regression with the larger number of points is used. - k_{el} must be positive, and calculated from at least three data points.
MRT	/h	
(single dose, non-infusion)
 $\text{MRT} = \text{AUMC}_{0-\infty} / \text{AUC}_{0-\infty}$ 
(single dose, infusion)
 $\text{MRT} = \text{AUMC}_{0-\infty} / \text{AUC}_{0-\infty} - T_{inf}/2$ 
(steady state)
 $\text{MRT} = [\text{AUMC}_{0-\tau} + \tau \times (\text{AUC}_{0-\infty} - \text{AUC}_{0-\tau})] / \text{AUC}_{0-\tau}$ 
AUMC_{0-∞}: area under the first moment curve extrapolated to infinity AUMC_{0-τ}: area under the first moment curve over the dosing interval AUC_{0-τ}: area under the concentration-time curve over the dosing interval T_{inf}: duration of infusion

V _z /F	L	
(single dose)
 $V_z/F = CL/F/k_{el}$ 
(steady state)
 $V_z/F = CL_{ss}/F/k_{el}$
Number of k_{el} points	—	will be determined using number of points used in computing k_{el} . If k_{el} cannot be estimated, zero.
Lower Limit of k_{el}	h	will be determined using lower limit on time to be included in the calculation of k_{el}
Upper Limit of k_{el}	h	will be determined using upper limit on time to be included in the calculation of k_{el}

[REDACTED]

[REDACTED]

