## 10. Assessment Methods and Criteria

### 10.1 Pharmacokinetics

Plasma concentrations of unchanged edaravone, sulfate conjugate and glucuronate conjugate will be measured to calculate  $AUC_{0-t}$ ,  $AUC_{0-24}$ ,  $AUC_{0-\infty}$ ,  $C_{max}$ ,  $t_{max}$ ,  $t_{1/2}$ ,  $Kel$ ,  $MRT,*$   $CL/F,*$   $V_z/F,*$  and  $V_{ss}/F*$  by non-compartmental analysis (\*: calculate only for unchanged edaravone). Urine concentration will be measured to calculate  $Ae$ ,  $Ae\%$ , and  $CL_r/F*$  (\*: calculate only for unchanged edaravone). The detailed calculation method for each parameter will be described in the Statistical Analysis Plan.

The drug concentration measurement site will separately create a protocol for concentration measurement by the start of measurement and perform measurement according to it. The site will create a measurement result report.

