1. INTRODUCTION

This statistical analysis plan (SAP) is based on the final protocol (v1.0) dated 1-Nov-2019. The plan covers statistical analysis, tabulations and listings of the study data to investigate the pharmacokinetics (PK) and safety. The study is evaluable in 6 subjects and may be completed before a sample size of 9 subjects is reached.

The SAP is prepared by Mitsubishi Tanabe Pharma Corporation (MTPC). The statistical analysis and production of the outputs described in the SAP and QC will be conducted by [REDACTED]. The final analysis and outputs will be checked and approved by MTPC Data Science Department.

Any statistical analysis details described in this document supersede any description of statistical analysis in the protocol.

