2.3. Pharmacokinetic Assessments

- (1) Drug concentration (in plasma and urine)

Unchanged edaravone, sulfate conjugate, and glucuronide conjugate

- (2) Pharmacokinetic parameters

Unchanged edaravone: AUC_{0-t}, AUC₀₋₂₄, AUC_{0-∞}, C_{max}, t_{max}, t_{1/2}, k_{el} MRT, CL/F, V_z/F, V_{ss}/F, Ae, Ae%, CL_R

Sulfate conjugate and glucuronide conjugate: AUC_{0-t}, AUC₀₋₂₄, AUC_{0-∞}, C_{max}, t_{max}, t_{1/2}, k_{el}, Ae, Ae%

Sum of unchanged edaravone and metabolites: Ae%

(t: Final concentration measurable time point)

Other PK parameters (for all PK profiles for which the k_{el} has been calculated): AUC%_{ex}, Adjusted R², Number of k_{el} points, Lower limited of k_{el}, Upper limiter of k_{el}

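### Does the kel row of SAP Appendix 1 need to rank visual inspection against the adjusted-R² search?

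*SAP*

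**What the plan says.** Protocol 10.1 leaves the method to the SAP: "The detailed calculation method for each parameter will be described in the Statistical Analysis Plan". The SAP gives it in the kel row of Appendix 1, which contains two statements on how many points enter the log-linear regression.

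- First: "The number of data points included in the regression will be determined by visual inspection".
- Then: "During the analysis, this calculation method repeats regressions using the last three points with non-zero concentrations", followed by four, five and so on. An adjusted-R² formula is given. "The regression with the largest adjusted" R² is kept. A tie within 0.0001 goes to the larger number of points, and tmax is excluded.

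The minimum number of points also appears twice: "Wherever possible, a minimum of 3 data points will be used in the estimation of" kel, and, as a closing condition, kel "must be positive, and calculated from at least three data points".

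SAP 7.1.3.2 lists what is not calculated when kel is unavailable: t1/2, AUC0-∞, AUC%ex, CL/F, MRT, Vz/F and Vss/F. SAP 2.3 adds a diagnostic set, "Other PK parameters (for all PK profiles for which the" kel was calculated: AUC%ex, adjusted R², the number of points and the time limits of the fit. SAP 8.4.2 has these listed but not summarized.

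**The concern.** A search that selects the number of points leaves nothing for inspection to determine, so on a literal reading the row fixes one quantity by two rules and ranks neither. No other section does so: SAP 8.4.2 says only that the analysis is non-compartmental, and SAP 11 names the software without a point-selection setting.

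The minimum raises a similar doubt. The softer wording seems to leave room for a two-point kel; the stricter one does not.

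At stake is the reproducibility of t1/2, Vz/F and, through MRT, Vss/F in individual subjects. One party produces the outputs, and under SAP 1 "The final analysis and outputs will be checked and approved by" the sponsor's data science department. Two people following the same row could therefore report different half-lives for the same subject.

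**Working it through.** **1. What the row lets an analyst do.** The visual sentence gives no criterion. The search has a starting set, a formula, a tie rule, an exclusion and a positivity condition. It starts at three points, so it never returns two. With fewer than three usable points kel is not determined, SAP 7.1.3.2 drops its dependents, and Appendix 1 sets the number of points to zero. No step in the row produces a two-point kel.

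**2. How many windows compete.** Protocol section 1 (Clinical Study Results) gives a suspension tmax of 0.4 to 0.8 h. Protocol 9.2.4.1 samples at 0.25, 0.5, 1, 2, 4, 8 and 24 h.

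- Observed peak at 0.5 h: 1, 2, 4, 8 and 24 h remain, giving three windows (last 3, 4 or 5 points).
- Peak at 1 h: two windows.
- 24 h sample below quantification: two windows (peak at 0.5 h) or one (peak at 1 h), and with one the rules cannot differ.

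**3. Size, rule against rule.** The documents give no concentrations or LLOQ. From them come only the sampling times, the Appendix 1 formulas and the terminal t1/2 range of 5.1 to 11.8 h. The following are assumed:

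- C(t) = Σ Aᵢ·ka/(ka − λᵢ)·(exp(−λᵢt) − exp(−ka·t)), with ka = 4/h.
- Half-lives 0.4, 1.5 and 5.1 / 8 / 11.8 h; amplitudes 1 : 0.2 : 0.02.
- Log-normal noise, all samples quantifiable, 9000 simulated subjects per setting (1000 studies of 9).
- The by-eye choice is always 4, 8 and 24 h.

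Noise-free t1/2 (h) by window:

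| Terminal t1/2 | 3 points | 4 points | 5 points | Search picks |
|---|---|---|---|---|
| 5.1 | 3.52 | 3.11 | 2.79 | 3 |
| 8 | 4.95 | 4.12 | 3.53 | 3 |
| 11.8 | 6.41 | 5.03 | 4.16 | 3 |

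Without noise the two rules agree. With noise (terminal t1/2 5.1 / 8 / 11.8 h):

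| Noise CV | Subjects whose points differ | Shift in geometric-mean t1/2 |
|---|---|---|
| 5% | at most about 0.2% | about 0% |
| 12% | 3.8 / 6.4 / 11.8% | 0.4 / 1.1 / 3.1% |
| 20% | 15 / 19 / 27% | 1.6 / 3.7 / 8.5% |

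At 12% noise, at least one of 9 subjects differs in 30 / 44 / 67% of simulated studies. As a check, 1 − (1 − p)⁹ with p = 0.038, 0.064 and 0.118 gives 29, 45 and 68%. In the affected subjects t1/2 differs by a median factor of 1.11 / 1.17 / 1.25.

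The low-noise result depends on the profile. A second assumed profile with faster early phases (half-lives 0.25 and 1.2 h, peak at 0.25 h) has the search leave three points in 1 − 0.976 = 2.4%, 1 − 0.963 = 3.7% and 1 − 0.878 = 12.2% of subjects at 5% noise.

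**4. Why AUC0-∞ hardly moves.** AUC0-∞ = AUC0-t + Clast/kel, so only the tail changes. In the second profile with terminal t1/2 11.8 h, the tail is 3.72% of 953.2 = 35.5 with three points and 2.96% of 945.7 = 28.0 with four. The difference of 7.5 is 7.5/945.7 = 0.8% of AUC0-∞, while t1/2 changes by 6.71/5.30 = 1.27 and Vz/F by 1067/850 = 1.26. Over a grid of 27 variants of the first profile, three against four points changes AUC0-∞ by at most 1.7% and t1/2 by a factor of 1.10 to 1.34. MRT and Vss/F were not computed; MRT weights the tail by time and would move more than AUC0-∞.

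**The case for a change.** The best case for amending is that an analyst should not have to infer precedence. t1/2 is a planned parameter, named in Protocol 13.4.2, and at 12% noise it is quite likely that at least one of nine subjects would have a different t1/2 under the two rules. The listed diagnostics show which points were used, but not whether leaving the search was allowed or why it was done. One sentence would settle it. A by-eye window of five points would change t1/2 by a factor of 1.20 to 1.70 against three points.

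Part of this stands: the SAP does not rank the two statements, and the softer wording of the minimum is loose. The rest carries less weight. With plasma concentrations, adjusted R², point count and time limits all listed, the checker can rerun the search and see any departure. The 1.20 to 1.70 range needs the 1 h and 2 h samples to be placed by eye in what the row calls the terminal phase, for a suspension whose elimination the protocol describes as three-phase. That would contradict the row's own definition, so it is not a fair picture of visual inspection.

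**Conclusion.** The wording is untidy, but no change to the plan follows. The sensible reading is that the adjusted-R² search selects the points, someone looks at each fit, and three points are required. The row's own steps support that reading, and either rule gives a usable descriptive kel.

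The effect is confined to individual t1/2, Vz/F, MRT and Vss/F. In the first assumed profile, geometric-mean t1/2 moves by about 0% at 5% noise, 0.4 to 3.1% at 12% and 1.6 to 8.5% at 20%. AUC0-∞ and CL/F are nearly unchanged, and Cmax, tmax, AUC0-t and Ae are untouched. There is no hypothesis test, and Protocol 6.1 says the sample size does not rest on a calculation, so no error rate or conclusion depends on the choice. Ranking the two statements would record what an analyst would do anyway.

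The sizes rest on assumed profiles and noise. The absence of any link from kel to Cmax, tmax, AUC0-t and Ae does not.
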